3. A limited control set using listening to oral reading of the lyrics and silent reading of the written lyrics with observation of pointing to written lyrics (no music).

Dependent Variables:

The dependent variable was defined as silent reading/comprehension of targeted words/phrases by pointing to words/phrases in a phrase completion exercise without music. The dependent variable was kept constant for all three conditions.

Dependent Measures

Measurement of the dependent variable consisted of both direct systematic observational recording (DSOR) and treatment record video (for reliability/procedural fidelity assessment) of percentage correct over time (including follow-up) and trials- or sessions-to-criterion.

Research Design

An AATD was used for comparison of two separate but similar conditions when the effects may be non-reversible (see Gast & Ledford, 2014, pp. 324-332). Time between sessions was at least a day.

“Criteria:

1. Behaviors must be non-reversible—the behaviors will continue to be performed after instruction has stopped.
2. Behaviors should not be in the participants' repertoire.
3. Behaviors must be independent, meaning one behavior set/chain can be acquired without influencing performance on other behavior sets/chains.
4. Behaviors also must be functionally equivalent, meaning behaviors are likely to be influenced by the same environmental variable (e.g., the instructional strategies being studied).
5. *Behavior sets/chains must be of equal difficulty.* The dependent variable in this investigation will be phrases acquired, but three different sets will be required to fulfill the requirement that the behaviors are independent. To ensure that they are of equal difficulty, they must all be assessed for word complexity at a minimum.

Randomizing items between treatment conditions should result in a relatively equal distribution of difficulty” (Romer, Billingsley, & White (1988).

Procedures

All songs were pretested for familiarity and positive valence by questioning the participants (i.e. Do you know this song? Do you like it?). Response data was recorded. All songs perceived as not liked were eliminated and substitutions made; the new songs were then also pretested for familiarity and positive valence. Songs that were not familiar but were liked were noted but not changed.

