During the baseline (A) all 25 phrases (Appendix C) were tested using the phrase completion task (Appendix D). Both correct responses and participation were verbally reinforced, as is required in an AATD. Results were analyzed by the SLP to ensure that the sets were of equal difficulty for each participant using two different procedures. First, logical analysis of the linguistic characteristics of the phrases was completed, including the number of words, the number of syllables in the words, the number of consonant blends in the words, and the number of contractions. Second, experimental evaluation of the number of error responses in each set during the baseline phase was completed, and without changing the items or responses, the set assignment was manipulated to maximally equate the number of error phrases without significantly changing the equivalency of the linguistic characteristics. One phrase was shifted from set 1 to set 2 during the baseline phase. In the end, the number of error responses on baseline for set 1 was three, for set 2 was two, and for the control set was two.

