During the intervention (B), each song (music with lyrics) from set 1 (B1) was played in its entirety. When the targeted verse or chorus played, the written lyrics were simultaneously shown along with the song lyrics. The SLP pointed to the words of the targeted verse/chorus which was silently observed by the participant as they were sung. This was repeated for all ten songs. The phrase completion task was then presented, including the total 25 phrases, without music. The participant silently or orally read the phrase and circled the phrase completion choice. Correct responses were randomly verbally reinforced. Error responses were followed by verbal modeling and pointing to the correct choice by the SLP. The next session, each song (music with lyrics) from set 2 (B2) was played in its entirety. After the song played, the written lyrics from the targeted verse or chorus were presented. The SLP pointed to the words of the targeted verse/chorus which was silently observed by the participant. This was repeated for all ten songs. The phrase completion task was then presented, including the total 25 phrases. The participant silently or orally read the phrase and circled the phrase completion choice. Correct responses were randomly verbally reinforced. Error responses were followed by verbal modeling and pointing to the correct choice by the SLP. This was repeated for all ten songs. For all interventions, the number of correct responses were tallied on a LaPoint Base 10 form and the percent correct entered on the graph for that day. The same procedures were repeated, alternating procedures on sets 1 and 2 on subsequent treatment visits, until a criterion of 9/10 (90%) x 3 consecutive visits was reached on both sets. It was predetermined that if the criterion was not reached on one of the intervention sets, defined as no increase in percentage correct x 3 consecutive visits, that intervention would be considered to be limited in effectiveness and discontinued. Every third session was digitally recorded for a reliability check by the trained assistant. When both of the sets (B1 and B2) had been acquired or one acquired and the other discontinued, the number of sessions to criterion were counted for each intervention.

Potential Threats to Internal Validity

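### Retention and sessions to mastery cannot be compared with the control as written: one uses raw counts from sets of apparently unequal size, the other has no control criterion; a smaller starting gap also touches set 1 v set 2

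*Combined protocol and SAP*

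**What the plan says.** **Sets.** Baseline tests 25 phrases. The Procedures describe ten songs for each music set. Under Independent Variable the third condition is "A limited control set using listening to oral reading of the lyrics". After baseline testing "the set assignment was manipulated to maximally equate the number of error phrases", and one phrase was moved from set 1 to set 2. The result was that "the number of error responses on baseline for set 1 was three, for set 2 was two, and for the control set was two".

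**Mastery.** Treatment continues "until a criterion of 9/10 (90%) x 3 consecutive visits was reached on both sets". The visit schedule is given as "alternating procedures on sets 1 and 2 on subsequent treatment visits". A music condition is discontinued if there is "no increase in percentage correct x 3 consecutive visits". Sessions to criterion are then counted for each of the two interventions.

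**Testing.** At each visit, "The phrase completion task was then presented, including the total 25 phrases". Errors are followed by modeling of the correct choice.

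**Retention.** Dependent Measures lists "percentage correct over time (including follow-up) and trials- or sessions-to-criterion". Outcome Measures and Time Points instead treats retention as a simple count of items.

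**Comparison.** The last item of Data Analysis takes sessions to mastery and retention together. It analyses both by differences between the control and the two music conditions.

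**The concern.** The control set is the plan's stated guard against history and maturation effects. On these two outcomes it can do that job only if it is scored on the same footing as the music sets. A raw count from a smaller set has a lower ceiling, so the music sets can come out ahead through size alone. A sessions figure for a set with no criterion and no visit schedule cannot be computed.

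The contrast between the two music sets has a milder problem. The plan says that its design tests efficiency, and sessions to criterion is the measure of it. If one set starts further from 9/10, part of any difference in sessions is starting score rather than treatment. The plan makes no allowance for this when it counts sessions.

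**Working it through.** **Inputs from the document.** 25 phrases; ten songs per music set; criterion 9/10 on three consecutive visits; baseline errors 3, 2 and 2. The error counts are observed data and the item-level appendices are not in the available text, so they cannot be recomputed.

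**Inferred sizes.** One scored phrase per song and the 9/10 criterion give 10 and 10. The control is then 25 − 10 − 10 = 5.

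| Set | Baseline | Needed for 9/10 | Most items retainable | Largest gain |
|---|---|---|---|---|
| 1 | 7/10 = 70% | 9 − 7 = 2 | 10 | 30 points |
| 2 | 8/10 = 80% | 9 − 8 = 1 | 10 | 20 points |
| Control | 3/5 = 60% | not defined | 5 | 40 points |

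**Retention.** Full recall gives 10, 10 and 5 items but 100% in every set. A music set that falls to 6/10 is below its baseline of 7/10 or 8/10. It still exceeds a control at 5/5 on the count (6 v 5), while percent gives 60% v 100%. The two definitions can therefore rank the sets in opposite order.

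**Sessions to mastery.** The criterion and the alternation of visits name sets 1 and 2 only. On five phrases 90% is 4.5, which is not a possible score. All 25 phrases are tested at every visit, so the text does not show which visits would count as control sessions.

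**Set 1 v set 2.** The document gives no learning rate, so p is an assumption. Let each missed phrase be learned with chance p on each visit day, equally in both sets, with no lapses or lucky guesses. Errors on all 25 phrases are corrected at every visit, so a missed phrase also has a chance on the other condition's day. Between counted visits that chance is q = 1 − (1 − p)². With k phrases missed, the chance that j are learned is C(k,j) q^j (1 − q)^(k−j). A set reaches 9/10 when at most one is missed and completes two visits later. It is discontinued after three successive visits without a gain while still below 9/10. Means are among sets that reach criterion; both sets are timed alike, so order is ignored.

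| p | q | Set 1 mean visits | Set 2 mean visits | Gap | Both reach criterion |
|---|---|---|---|---|---|
| 0.1 | 0.19 | 4.88 | 3.73 | 1.2 | 47% |
| 0.2 | 0.36 | 4.16 | 3.47 | 0.7 | 88% |
| 0.3 | 0.51 | 3.65 | 3.27 | 0.4 | 98% |
| 0.5 | 0.75 | 3.17 | 3.07 | 0.1 | nearly 100% |

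Hand check, set 2 at p = 0.1: the chance of learning at least one of two is 1 − 0.81² = 0.3439. First success at visits 1, 2 and 3 has probability 0.3439, 0.2256 and 0.1480, total 0.7176. The mean is (0.3439 + 2 × 0.2256 + 3 × 0.1480)/0.7176 = 1.73, plus 2 = 3.73.

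At p = 0.5, 80% of comparisons are ties. If learning happened only on a set's own days (q = p), the gaps would be 1.4, 1.1, 0.8 and 0.4 visits.

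**Sensitivity to size.** If the moved phrase left 9 and 11, a 90% rule needs 9 and 10 correct from starts of 6 and 9, so the gaps are 3 v 1. If the sets are 11 and 9, it needs 10 and 9 from starts of 8 and 7, so the gaps are 2 v 2. The control is 5 in both cases.

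**The case against.** **Set sizes.** The phrases are in an appendix that is not in the available text, and it may state the sizes. This stands: 10, 10 and 5 are inferred, so no omission from the plan is claimed. The conflict between the two retention scales and the missing control criterion do not depend on the sizes.

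**Retention and control.** One can say that percentage correct is already named for follow-up, that the count appears in a discussion of measurement scales, and that the sentence on sessions is only loosely worded. That makes both points clarifications, but needed ones. The later section defines the outcome as a count, and Data Analysis names the control as comparator for both outcomes.

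**Starting gap.** Five errors cannot be split equally between two sets. The plan equated them as far as possible, disclosed the remainder and graphs daily percent correct. It does not say whether the errors come from one baseline session or several, and a one-phrase difference on a multiple-choice task may be partly noise. All of this stands.

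**Stronger readings.** A reader might infer a penalty of about three visits for set 1, or that B1 and B2 cannot be ranked at all. The larger figure (3.1 visits at p = 0.1) ignores both the corrective feedback on all 25 phrases and the discontinuation rule. Ranking remains possible once the gaps are shown. Nor does the 3 v 2 imbalance come from equating counts instead of rates: on the inferred sizes, sets 1 and 2 are equal.

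**Conclusion.** The main point holds. Retention has two definitions that can disagree on rank, and sessions to mastery cannot be computed for the control. The definitional conflict and the missing criterion follow from the text; the 10 v 5 distortion rests on inferred sizes.

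The secondary point is a tendency, not a demonstrated bias. With 10 phrases per music set and identical learning, raw sessions lean toward set 2 by roughly 1.2 visits under slow learning and 0.1 under fast learning. It rests on an assumed learning rate, equal learning on both conditions' days and one set of error counts for an unnamed participant. It need not recur, or favor the same condition, in other participants.

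A reader might infer that the whole analysis is compromised. The document does not support that: daily percent correct and the two-standard-deviation band, which is referenced to baseline, are less exposed. The point concerns two outcomes and should be fixed.

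**What to change.** 1. **Retention.** Reconcile Dependent Measures with Outcome Measures by analysing retention as percent of each set, with that set's baseline percent beside it.
2. **Control.** Drop it from the sessions comparison. Compare it on percent correct or change from baseline, showing each set's ceiling (30, 20 and 40 points on the inferred sizes).
3. **Set 1 v set 2.** For each participant, report set size and baseline gap beside sessions to criterion, show any discontinued set as such, and interpret a B1 v B2 difference in that light.

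The cost is wording and reporting only, with no new phrases, visits or data. The downside is in item 2. One phrase is worth 20 points in a five-phrase control and 10 in a music set, so the measure is coarse. Change in percent also favors the set with the higher baseline error rate. For example, at p = 0.2 per visit over eight visits, 1 − 0.8⁸ = 83% of missed phrases are learned in every set, yet the gains are 25, 17 and 33 points for set 1, set 2 and control. The ceilings must therefore be shown.

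### Phrase set and starting order are tied to the music condition with no reversal described, so sessions-to-criterion cannot separate them

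*Combined protocol and SAP*

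**What the plan says.** All references are to the Combined protocol and SAP.

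- **Pairing and order (Procedures).** Set 1 is labelled B1, with lyrics shown while the song plays. Then: "The next session, each song (music with lyrics) from set 2 (B2) was played in its entirety", with lyrics shown after the song. Treatment continues by "alternating procedures on sets 1 and 2 on subsequent treatment visits". The end point for this is given as "until a criterion of 9/10 (90%) x 3 consecutive visits was reached on both sets". A music condition is dropped if the criterion is not reached, "defined as no increase in percentage correct x 3 consecutive visits". Every visit tests all 25 phrases and corrects errors.
- **Equating (Procedures).** Sets are compared on linguistic features and baseline errors for each participant, and "the set assignment was manipulated to maximally equate the number of error phrases". "One phrase was shifted from set 1 to set 2 during the baseline phase". The result was that "the number of error responses on baseline for set 1 was three, for set 2 was two, and for the control set was two". Songs can also differ by participant: "All songs perceived as not liked were eliminated and substitutions made".
- **Counterbalancing (Potential Threats to Internal Validity).** It is called necessary, in the context of sequence and carryover effects. No scheme is given.
- **Use of the session count.** Research Design describes a comparison of two conditions, and Procedures counts sessions to criterion for each intervention. The last item of Data Analysis instead sets the control treatment against the two target conditions. It plans group means once at least four participants have completed.
- **Stage (Sample Size).** The first two participants are reported, of a minimum of four and a maximum of ten.

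**The concern.** Sessions-to-criterion is the plan's direct measure of which music condition teaches faster. If set 1 always carries simultaneous music and always goes first, a difference in that count has three possible sources: the condition, the phrases, or the order. Order has a plausible route. Because errors on all 25 phrases are corrected at every visit, set 2 has already had a round of correction before its own first session.

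The criterion also lies close to baseline, so a difference of one phrase can matter. At stake is whether the efficiency statement, for single participants and for the pooled means, can be credited to the music condition.

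**Working it through.** **1. Can condition be separated from set and order?** Let d be sessions for simultaneous music minus sessions for priming. For a participant run as described, d = c + x + u. Here c is the condition effect, x is a set-plus-order effect shared by all participants, and u is that participant's own residual. With pairing and order both reversed, d = c − x + u. Averaging over n participants:

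mean d = c + x × (n as described − n reversed)/n + mean u

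| As described : reversed | Share of x left in the mean |
|---|---|
| 4:0 | (4 − 0)/4 = 1 |
| 3:1 | (3 − 1)/4 = 0.5 |
| 2:2 | (2 − 2)/4 = 0 |

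If u is centred on zero, its mean shrinks as n grows; x at 4:0 does not. Equivalently, with columns for intercept, condition and set, the fixed pairing gives a design matrix of rank 2 out of 3 at any n. Reversing half the participants gives rank 3. This step needs no learning model.

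**2. The reported baseline, as illustration.** The 3/2/2 counts are observed and cannot be reproduced, because the item data are not in the text. The criterion checks: 9/10 = 90%. Two inferences are needed:

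- Ten phrases per music set. This fits the ten songs and the 9/10 criterion, but final sizes after the shift are not stated.
- Counts are per test.

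Then set 1 starts at 7/10 and needs 9 − 7 = 2 phrases; set 2 starts at 8/10 and needs 9 − 8 = 1.

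**3. Size of the lean.** Assumptions: each missed phrase is learned with the same chance h per session in both conditions and is then kept; the discontinuation rule means three successive visits without a rise; completion is the first visit at 9/10 plus two more. Write q = 1 − h and take h = 0.2.

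- *Set 2.* The chance of first reaching 9/10 at visits 1, 2, 3 is 0.36, 0.2304, 0.1475 (each is the last times q² = 0.64). The total is 0.738, so q⁶ = 0.262 are discontinued. Mean = (0.36 + 2 × 0.2304 + 3 × 0.1475)/0.738 + 2 = 3.71.
- *Set 1.* P(discontinued) = q⁹ + (1 − q⁹) × [3hq²/(1 − q³)] × q⁶ = 0.134 + 0.866 × 0.787 × 0.262 = 0.313. The same recursion gives a mean of 4.84 among those reaching criterion.
- *Gap.* 4.84 − 3.71 = about 1.1. Both reach criterion in 0.738 × 0.687 = 51% of cases.

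| h | Set 1 v set 2, mean sessions | Gap | Both reach criterion |
|---|---|---|---|
| 0.2 | 4.8 v 3.7 | 1.1 | 51% |
| 0.3 | 4.4 v 3.6 | 0.8 | 78% |
| 0.5 | 3.7 v 3.3 | 0.4 | 98% |

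At h = 0.1 both sets reach criterion in only 15% of cases, so no lean is claimed there.

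**4. Guessing.** The task is multiple choice. With assumed guessing of 1/4 to 1/3, 35% of phrases unknown and lapses of 0 to 5%, conditioned on 3 v 2 observed errors, simulated gaps at h = 0.2/0.3/0.5 fall to about 0.8–0.9, 0.5–0.6 and 0.2–0.3. Simultaneous music then finishes first in about 20 to 37% of completed pairs, against 13 to 15% without guessing or lapses. The lean remains, but finishing order is far from assured.

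**5. If the counts are totals.** The two-standard-deviation band in Data Analysis implies several baseline points. Over, say, three tests, misses average 3/3 = 1.0 and 2/3 = 0.67 per test. Both sets could start at or above 9/10, and the lean could be nil.

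**The case against.** **The design has its own safeguard.** Set and condition are inseparable within one participant in any design of this type, and equating is the intended protection. The plan equates in two ways, for each participant. The design criteria quoted in Research Design add that randomising items should roughly equalise difficulty. This stands in part: equating reduces the problem. But Procedures describes reassignment after baseline rather than randomisation, and matching on features and a few errors does not establish equal learnability.

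**Pooling will deal with it.** Songs and sets can differ by participant, so part of the set effect will average down. A reader might infer that pooling can never help; the documents do not support that. Only a shared effect of set or order persists.

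**Counterbalancing may have been done.** A reader might infer that none was used. The text shows only that none is described. The wording about alternating procedures could be read as swapping conditions between sets, but the B1 and B2 labels and the per-intervention count point to alternating visits.

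**The session comparison may be against control.** Data Analysis can be read that way, while Research Design and Procedures support music v music. The ambiguity is real and the plan should settle it.

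**3 v 2 is trivial.** It is one phrase, in one baseline, with the participant not stated (Fisher p = 1.0 for 3/10 v 2/10). Accepted: it illustrates the point and does not carry it.

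**Conclusion.** The concern holds for a music v music comparison of sessions-to-criterion. As written, the plan cannot separate condition from phrase set or starting order, and a shared set or order effect passes in full into group means at any number of participants. Its size and direction are unknown. This rests on reading the alternation as alternating visits and on no reversal being described elsewhere.

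The baseline lean is secondary: about 0.2 to 1.1 sessions towards priming at h = 0.2 to 0.5, with or without guessing. It depends on ten phrases per set, per-test counts and equally effective conditions. If the shift left nine and eleven phrases, the distances to 90% change and this range does not apply.

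A reader might infer that the study is biased towards priming. The documents do not support that: there is one unidentified baseline, nothing shows that the gap recurs, and it may be nil. Percent correct, retention, BDAE scores and comparisons with control are outside this point.

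**What to change.** 1. For every further participant, once that participant's sets are final, use a prepared list to randomise or counterbalance which set goes with which music condition and which condition starts. Pairings should end equal, counting those already run. If the first two ran as described, reversing pairing and order for the next two gives 2:2 at four.
2. Beside sessions-to-criterion, report each participant's final set sizes, baseline errors (per test or total) and phrases needed to reach 9/10 in each music set. Caveat the efficiency comparison for participants already run under the fixed pairing.
3. State whether the session comparison is music v music, each against control, or both.

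The cost is a few protocol sentences, a short list and slightly more set-up work, with no extra visits or staff. The downsides are a weaker efficiency statement for participants already run, balance only across participants and not within one, and little precision at four.

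### Read as totals, the baseline counts mean about 18 of 25 phrases were already answered correctly, so sessions to criterion rests on very few phrases and is weak evidence of acquisition

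*Combined protocol and SAP*

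**What the plan says.** Research Design adopts a list of criteria for the adapted alternating treatments design. One is that "Behaviors should not be in the participants' repertoire". The same list says that "The dependent variable in this investigation will be phrases acquired".

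Under Procedures, all 25 phrases are tested at baseline. The sets are then made comparable as follows: "without changing the items or responses, the set assignment was manipulated to maximally equate the number of error phrases". One move is reported: "One phrase was shifted from set 1 to set 2 during the baseline phase". The result is that "the number of error responses on baseline for set 1 was three, for set 2 was two, and for the control set was two".

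In the treatment phase the full 25-phrase task is given at each visit, and treatment alternates between the two music sets "until a criterion of 9/10 (90%) x 3 consecutive visits was reached on both sets". Sessions to criterion are then counted for each intervention. No section limits the sets, or the score, to phrases missed at baseline, and none explains a departure from the repertoire criterion.

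**The concern.** A phrase that the participant already completes correctly cannot be shown to have been acquired under either music condition. Here such phrases seem to be the majority. They were kept, and they count towards mastery.

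Two things are at stake. First, sessions to criterion is the efficiency comparison between the music conditions, and it would turn on a handful of multiple-choice items. Second, the graphed percentage starts high, so there is limited room for a difference between conditions to show. Neither problem comes from the uneven start of three errors against two; both would remain with two errors in each music set.

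**Working it through.** **Inputs.** From Procedures: 25 phrases; baseline errors 3, 2 and 2; mastery at 9/10 on three consecutive visits. Inferred: ten phrases per music set, from the 9/10 criterion and from "This was repeated for all ten songs", which leaves 25 − 20 = 5 for the control set. Assumed: 3 to 4 answer choices (Appendix D is not in the available text) and 8 visits per condition. The error counts are raw observations, so there is no derived figure of the plan's to reproduce.

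**Share already correct.** 3 + 2 + 2 = 7 errors; 25 − 7 = 18; 18/25 = 72%.

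**Could guessing explain the 18?** With k choices and p = 1/k, the guess-corrected number known is (18 − 25p)/(1 − p). This gives 11.0, 14.5, 15.7 and 16.3 of 25 for k = 2, 3, 4 and 5. Even with two choices, a large part of the material was known.

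**Distance to mastery.** Set 1: 10 − 3 = 7 correct, so 9 − 7 = 2 more are needed, with 30 points of headroom. Set 2: 10 − 2 = 8 correct, so 9 − 8 = 1 more, with 20 points of headroom. If the reported shift left 9 and 11 phrases, set 1 is at 6/9 and 90% requires 9/9 (three more); set 2 is at 9/11 and 90% requires 10/11 (one more). These are net gains: the other phrases must hold for three visits.

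**Mastery with no learning.** Let q be the chance of at least 9/10 on one visit, and f(n) the chance of three such visits in a row within n visits. Then f(0) = f(1) = f(2) = 0, f(3) = q³, and f(n) = f(n−1) + [1 − f(n−4)](1 − q)q³.

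- *Model A: baseline-correct phrases stay correct, missed ones are guessed.* With two missed, q = 1 − (1 − p)², which is 0.438 (4 choices) or 0.556 (3 choices). With three missed, q = 3p²(1 − p) + p³, which is 0.156 or 0.259.
- *Model B: every phrase independently correct at the baseline rate.* q = P(at least 9 of 10), which is 0.376 at 80% and 0.149 at 70%.
- *Model C: as A, but baseline-correct answers may also have been guesses.* The number known is (x − 10p)/(1 − p). An observed x = 8 gives 7.33 (4 choices) or 7.0 (3 choices); x = 7 gives 6.0 or 5.5. Fractions are handled by weighting the two adjacent whole numbers; for 7.33, (2/3)(0.020) + (1/3)(0.309) = 0.12.

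Results for f(8):

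| Model | Set at 8/10 | Set at 7/10 |
|---|---|---|
| A, 4 / 3 choices | 0.31 / 0.52 | 0.02 / 0.08 |
| B | 0.21 | 0.02 |
| C, 4 / 3 choices | 0.12 / 0.08 | 0.001 / 0.004 |

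With 5 visits instead of 8, model A for a set at 8/10 gives 0.18 (4 choices) and 0.32 (3 choices).

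**The case against.** Several stronger readings are tempting, and the documents do not support them.

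- *That at least 18 phrases were certainly known, for everyone.* The number of baseline tests is not given. If the counts are per-session averages, different phrases may have been missed on different days, and fewer than 18 may have been correct throughout. Sets were equated for each participant and Sample Size refers to two, but only one triplet appears; it may describe one of them.
- *That mastery by guessing has probability 0.31 to 0.52.* That is model A alone. It treats missed phrases as pure guesses and correct ones as permanently known on the same multiple-choice task. Allowing guesses on both sides gives about 0.08 to 0.12. The 8 visits are an assumption: the 17 visits under Human Rights Protections describe normal progress, not a cap to be halved. The rule that drops an intervention whose score stops rising could also end a run early.
- *That the two-standard-deviation band cannot be exceeded.* The upper limit reaches 100% only if the baseline SD is at least (100 − 80)/2 = 10 points for set 2, or (100 − 70)/2 = 15 points for set 1. No baseline SD is given.
- *That a mandatory rule is broken.* The repertoire criterion says should, where neighbouring criteria say must, and one could argue that a set at 70% to 80% is not yet in the repertoire because it falls short of 90%. But the outcome is counted in phrases, which favours the phrase-level reading.

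The Boston Diagnostic Aphasia Examination comparison before and after treatment does not depend on these sets and is unaffected. What stands is the unexplained conflict between the criterion and the retained phrases, and the small number of phrases that decide mastery. The rationale that baseline should show optimal performance explains reinforcing baseline responses; it does not explain keeping known items.

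**Conclusion.** The point holds in this limited form. With the counts read as totals, about 18 of 25 phrases (72%) were correct before any music, remained in the sets, and count towards 9/10. With ten-phrase music sets, mastery is a net gain of about two phrases in set 1 and one in set 2 (three and one with 9 and 11 phrases), within 30 and 20 points of headroom.

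Under the assumed 8 visits and 3 to 4 choices, the chance of reaching mastery with no learning is roughly 0.1 to 0.5 for a set at 8/10, depending on the model, and below 0.1 for a set at 7/10. These ranges show that the criterion can be weak for set 2; they do not estimate a false-positive rate for this study.

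Sessions to criterion is therefore weak evidence of acquisition, not worthless evidence. This should be fixed, but it does not invalidate the study.

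**What to change.** **Later participants.** In Procedures, before the sets are fixed and equated, replace each phrase answered correctly throughout baseline and test the replacement, using the substitute-and-retest step that the plan already applies to disliked songs. Remove the condition that items stay unchanged.

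**Participants already treated.** Keep the 9/10 result as planned. Add, for each participant and set, the number of baseline-missed phrases later answered correctly (for the reported triplet, out of 3, 2 and 2). Read the music-set counts against the control-set count: selecting phrases because they were missed brings regression to the mean, so some apparent gain is expected without learning. State whose baseline the triplet describes, how many baseline tests it covers, and the final set sizes. State also that the repertoire criterion was not met, so sessions to criterion is weak evidence of acquisition.

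**What not to do.** Do not redefine mastery on the missed phrases alone. With two or three items, 90% means all of them, which is coarser than 9/10 and carries the same regression to the mean.

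**Cost.** A larger pool of songs and phrases and possibly one more baseline test for later participants; for treated participants, a re-tally of existing item scores.
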